7.4 Prior Anti-Cancer Therapy

Prior anti-lymphoma therapies are coded according to WHODRUG and stored with Anatomical Therapeutic Class (ATC) codes and generic names.

The number of prior anti-lymphoma therapies, the best response to the most recent regimen, the primary reason the most recent regimen was discontinued, and the number of cycles for the most recent regimen will be tabulated.

New anti-cancer therapies are addressed in Section 9.2.

7.5 Prior Radiotherapy

Prior radiotherapies are coded according to WHODRUG and stored with Anatomical Therapeutic Class (ATC) codes and generic names.

The presence or absence of prior radiotherapy, the site of radiotherapy, the type of radiotherapy, and best response to prior radiotherapy will be tabulated.

7.6 Prior Surgery

Prior surgeries will be coded according to MedDRA. All prior surgery will be listed by subject.

8 Exposure and Compliance

8.1 Dose Level Cohorts

All subjects receiving investigational treatment during this open-label trial will receive GEN3009. Subjects in the Dose Escalation part will receive dose levels as assigned; all subjects in the Dose Expansion part are expected to receive the RP2D.

8.2 Dosage and Treatment Duration

Descriptive statistics for the number of cycles initiated will be presented overall and by dose level cohort or diagnosis cohort (as appropriate).

The cumulative dose, actual dose intensity, cumulative planned dose, planned dose intensity, relative dose intensity, and treatment duration will be presented by cohort, separately for Cycles 1-3, 4-9, and 10+. The completion status and withdrawal reasons (withdrew due to AE, withdrew due to PD, or withdrew due to other reason), and subjects with dose adjustments (reductions,

interruptions, or permanent discontinuations) and reasons for adjustments, will be summarized by treatment cycle and cohort.

The total treatment duration and total number of days in trial will be summarized by cohort.

Follow-up time will be calculated, as the time from first dose of trial treatment until the last contact date or date of death, whichever comes last. Follow-up time will be summarized with univariate statistics, without adjusting for censoring, and presented using mean, median, SD, minimum and maximum.

Exposure information will be listed by subject.

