9.2.2 Evaluations

Efficacy assessments will be conducted as specified in the visit assessment schedules (refer to [Table 2](#), [Table 3](#), [Table 5](#), [Table 6](#), [Table 10](#), and [Table 11](#) will include the following: imaging assessments (including hepatic involvement and splenic involvement [size by vertical: cranial to caudal]), bone marrow assessment (as applicable), physical exam including constitutional symptoms, ECOG performance status, MRD status, and other procedures as necessary. All efficacy assessments should be conducted throughout the trial until disease progression, the start of new anti-cancer therapy, death or withdrawal of consent from trial participation, whichever occurs first.

Response assessment for B-cell NHL will be according to revised response criteria ([Cheson et al., 2014](#)) (refer to [Appendix 7](#)) and for CLL according to the iwCLL ([Hallek et al., 2018](#)) (refer to [Appendix 8](#)).

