Imaging assessment schedules in both the Dose Escalation and Expansion are: at screening, on Cycle 2 (Week 6), Cycle 3 (Week 12), Cycle 5 (Week 18), Cycle 6 (Week 24), Cycle 9 (Week 36), Cycle 12 (Week 48), and every 24 weeks (Cycle 18, 24, etc.) thereafter until confirmation of disease progression is assessed by the investigator, the start of new anti-cancer therapy, withdrawal of consent, or death, whichever occurs first. All assessments will be determined from the first dose date and will follow the counting of calendar days and not the dosing cycles. Refer to [Table 29](#) for details. Refer to [Appendix 9](#) for PET positivity evaluation.

Additional imaging assessments may be performed at any time during the trial at the investigator's discretion to support the efficacy evaluations for a subject as necessary. Clinical suspicion of disease progression at any time requires a physical examination and imaging assessments to be performed promptly rather than waiting for the next scheduled imaging assessment.

Table 29 Imaging Assessments During Dose Escalation and Expansion

Subject Diagnosis	Imaging	Screening	On-treatment Assessment
B-cell NHL	FDG-PET CT	Required within 3 weeks (ie, 21 days) before Cycle 1 Day 1	Required at: Cycle 2 (Week 6±7 days), Cycle 3 (Week 12±7 days), Cycle 5 (Week 18±7 days), Cycle 6 (Week 24±14 days), Cycle 9 (Week 36±14 days) Cycle 12 (Week 48±14 days) then every 24 weeks thereafter (ie, Cycle 18, 24, 36±14 days, etc) until confirmation of disease progression, start of new anti-cancer therapy, withdrawal of consent, or death, whichever comes first
B-cell NHL including CLL	CT/MRI (neck, chest, abdomen, and pelvis) Note: For subjects with non-avid or variably FDG-avid tumors, CT scan with IV contrast of neck/chest/abdomen/p	Required within 3 weeks (ie, 21 days) before Cycle 1 Day 1	Required at: Cycle 2 (Week 6±7 days), Cycle 3 (Week 12±7 days), Cycle 5 (Week 18±7 days), Cycle 6 (Week 24±14 days), Cycle 9 (Week 36±14 days) Cycle 12 (Week 48±14 days)

Subject Diagnosis	Imaging	Screening	On-treatment Assessment
	elvis/additional known lesions will be performed MRI may be used to evaluate sites of disease that cannot be adequately imaged using CT		then every 24 weeks thereafter (ie, Cycle 18, 24, 36±14 days, etc.) until confirmation of disease progression, start of new anti-cancer therapy, withdrawal of consent, or death, whichever comes first

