9.3.6 Survival Status

Survival status will be assessed every 3 months via telephone contact, email, or on-site visit, after the last administration of GEN3009 and/or GEN3013 and will continue until the subject dies or withdraws from the trial. Data will be collected as reported by the subject regarding disease status, new anti-lymphoma treatment, any other malignancy other than the disease under study (ie, a second primary malignancy), and survival status, if available. If the subject is not available for this assessment, the response should be entered as “lost to follow up” ([Section 8.4](#)).

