5.3.3 Progressive Disease

Progressive disease must be confirmed by 2 consecutive scans, at least 4 weeks apart, as described in protocol 9.2.3.2.

5.4 *Calculation of durations and times to events*

Duration of an event occurring on or after first dose date, in days, is calculated as event end date – event start date + 1.

Durations in weeks will be calculated as durations in days divided by 7.

Durations in months will be calculated as durations in days divided by 30.4375.

Time from initial diagnosis will be calculated in months, from the initial diagnosis of the primary site to the first dose date: (first dose date – date of first diagnosis) /30.4375

Time from last anti-CD20 therapy to treatment with GEN3009 will be calculated in months, from the latest treatment end date of any agent administered as part of the last prior anti-lymphoma treatment that included an anti-CD20 compound to the first dose date: (first dose date – date of last anti-CD20 therapy +1) /30.4375

Total number of months on trial will be calculated as: (last contact date – first dose date + 1)/30.4375

Follow-up time will be calculated, in weeks, as: (date of last disease assessment by investigator – first dose date + 1) / 7.

Total treatment duration will be calculated in days as:

- If last cycle is Cycle 1, 2 or 3: last dose date – first dose date + 7
- If last cycle is Cycle 4 – 9: last dose date – first dose date + 14
- If last cycle is Cycle 10 or later: last dose date – first dose date + 28

Progression-free survival (PFS)

PFS is defined as the time in days from Day 1 of Cycle 1 to the day (+1) of first documented disease progression, or the day (+1) of death due to any cause, whichever comes first. Progression does not require confirmation (per Lugano criteria). PFS censoring will be based on Table C1 in Appendix C in the FDA Guidance for Industry: Clinical Trial Endpoints for the Approval of Non-small Cell Lung Cancer Drugs and Biologics [4].

Duration of response (DOR) will be calculated in days as:

DOR = date of first documented progressive disease or death from any cause – date of first response + 1.

In the absence of progressive disease or death, responders will be censored per the FDA censoring rule utilized for PFS, as presented in Appendix I. First response is defined as first documented occurrence of CR or PR (including any complete responses pending confirmation). DOR will only be calculated for those subjects achieving CR or PR.

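### SAP 5.4 and SAP 8.2 define follow-up time in conflicting ways, and the unadjusted median in 8.2 can understate how long subjects could have been observed

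*SAP*

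**What the plan says.** SAP 5.4 (Calculation of durations and times to events) gives this rule: "Follow-up time will be calculated, in weeks, as: (date of last disease assessment by investigator", minus the first dose date, plus 1, divided by 7.

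SAP 8.2 (Dosage and Treatment Duration) defines the same-named variable "as the time from first dose of trial treatment until the last contact date or date of death, whichever comes last", and gives no unit. It then sets the summary: "Follow-up time will be summarized with univariate statistics, without adjusting for censoring". The statistics listed are mean, median, SD, minimum and maximum.

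SAP 5.4 also has a third, closely related quantity: "Total number of months on trial will be calculated as: (last contact date", minus first dose, plus 1, converted to months. That is nearly the 8.2 definition under another name.

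The two end dates follow different rules in the protocol. Section 9.2.2: "All efficacy assessments should be conducted throughout the trial until disease progression, the start of new anti-cancer therapy, death or withdrawal of consent". Section 9.3.6: "Survival status will be assessed every 3 months via telephone contact, email, or on-site visit", continuing until death or withdrawal from the trial. Section 9.2.2.1 sets the later imaging visits at "Cycle 12 (Week 48), and every 24 weeks (Cycle 18, 24, etc.) thereafter".

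**The concern.** Two programmers working from this SAP could produce different follow-up tables, and both would be following it. The gap is systematic. A subject who progresses and lives on stops contributing under 5.4 but continues under 8.2. After Week 48, a subject in continuing remission can also differ by months, because scans are then 24 weeks apart.

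Separately, a plain median that treats death as the end of follow-up mixes survival with observation time. It falls as mortality rises, even when every subject had the same opportunity to be observed.

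This matters because no other planned summary states potential follow-up directly. SAP 1.2 times the primary expansion analysis only by a sufficient amount of time on study, and no minimum is set. A reader of DoR and PFS from single-arm cohorts of about 20 will look to median follow-up to judge maturity.

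**Working it through.** **1. Definitions side by side**

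| | SAP 5.4 | SAP 8.2 |
|---|---|---|
| Start | first dose | first dose |
| End | last investigator disease assessment | last contact or death, whichever is later |
| Unit | weeks | none stated |
| Shortened by progression | yes, assessments stop | no, survival contact continues |
| Shortened by death | yes | yes |

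Both definitions sit in the SAP, so the SAP's basis in protocol version 4.0 does not explain the conflict.

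**2. Inputs for the size**

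The documents state no median follow-up, target, accrual period or fixed cut-off, so there is no planned figure to reproduce. The calculation is illustrative.

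- Assumed: exponential survival time T with median m, and potential follow-up C uniform on (a, b) months.
- From protocol 2.1.1.2: 34 to 50% alive at 5 years after early relapse of follicular lymphoma (FL). Under an exponential, m = 60 × ln 2 / (−ln 0.34) = 38.6 months, and 60 months at 50%.
- From protocol 2.1.1.1: life expectancy of 3 to 4 months in relapsed or refractory DLBCL not responding to second-line treatment, used as a pessimistic bound.

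**3. The SAP 8.2 median**

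This is the median x of min(T, C), which solves P(T > x) × P(C > x) = 0.5, with P(T > x) = 2^(−x/m), P(C > x) = 1 below a, and (b − x)/(b − a) between a and b.

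With C on (12, 30), median potential follow-up is 21 months:

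- m = 6: x is below 12, so 2^(−x/6) = 0.5 and x = 6.0 months.
- m = 24: at x = 15.8, 2^(−15.8/24) × (30 − 15.8)/18 = 0.634 × 0.789 = 0.50, so x = 15.8 months.

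The shortfalls are 1 − 6/21 = 71% and 1 − 15.8/21 = 25%.

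FL-like survival at early cut-offs (simulated; m = 38.5 used for the lower bound):

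| C (months) | Potential median | m = 38.5 | m = 60 |
|---|---|---|---|
| 6 to 18 | 12.0 | 10.7 (11% short) | 11.2 (7% short) |
| 12 to 24 | 18.0 | 16.0 (11% short) | 16.7 (7% short) |

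At the pessimistic DLBCL bound (m = 3.5), the 8.2 median is 3.5 months against 12.0 or 18.0, a shortfall of about 71% or 81%.

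**4. The SAP 5.4 median**

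Further assumption: exponential time to progression with median m/2. Scans follow protocol 9.2.2.1 (Weeks 6, 12, 18, 24, 36 and 48, then every 24 weeks). Progression is recorded at the next scan if the subject is alive and before cut-off, and otherwise the last earlier scan counts. With C on (12, 30), the median falls on the Week 12 scan for m = 6 (84/30.4375 = 2.8 months) and on the Week 36 scan for m = 24 (252/30.4375 = 8.3 months). A second scan to confirm progression, as SAP 5.3.3 asks, is not modelled and would lengthen these figures.

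**5. Reverse Kaplan-Meier on the same data**

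With deaths censored and end of observation while alive taken as the event, the large-sample median is about 21 months for both m = 6 and m = 24. It recovers potential follow-up.

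**6. Small samples**

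With C on (12, 30) and m = 6, about 90% of subjects have died by cut-off. In simulated cohorts of 20, the reverse Kaplan-Meier median was not estimable in about 23%; in the rest, its central 95% range was about 13 to 29 months. With 3 subjects it was not estimable in about 71%.

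**The case against.** The strongest reply is that SAP 8.2 sits under Exposure and Compliance and says openly that it describes observed time. Observed time is a legitimate description, and nothing in the SAP calls it the maturity measure for the efficacy endpoints. Maturity can also be read in part elsewhere: SAP 10.2.1 reports numbers with events and numbers censored for DoR, with Kaplan-Meier estimates at monthly intervals, and PFS and OS follow the same presentation. This stands as a reason to keep and relabel the plain summary. It does not resolve the two definitions, and it leaves potential follow-up unreported.

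Three stronger readings are tempting and not supported.

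- A reader might infer that reported follow-up will always be far too short. The size depends on mortality, cut-off and which definition is used. The documents fix neither mortality nor the cut-off, and FL-like survival at an early cut-off gives only 7 to 11% under 8.2.
- A reader might infer that progression shortens both versions. Under 8.2 it does not, because survival contact continues after progression.
- A reader might infer that efficacy estimates are biased. ORR and CR rate do not use follow-up time. DoR, PFS and OS have their own censoring rules in SAP 5.4 and Appendix I.

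It is also fair that reverse Kaplan-Meier is uninformative in dose-level cohorts of 1 to 4 subjects; the fix is limited accordingly.

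**Conclusion.** The conflict between SAP 5.4 and SAP 8.2 is established by the text alone. The direction of the second problem is also certain: an unadjusted median that counts death as the end of follow-up cannot exceed median potential follow-up and can fall below it.

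The size is conditional. It is large where mortality is high (6 against 21 months), moderate at median survival of 24 months (15.8 against 21), and small for FL-like survival at early cut-offs. The 5.4 version is shorter still, at about 2.8 and 8.3 months in the first two cases. All these figures rest on exponential times and uniform potential follow-up, and the 5.4 figures also on progression at half of median survival.

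The consequence is confined to how data maturity is described. The change should be made, but no endpoint estimate or dose decision depends on it.

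**What to change.** In the SAP:

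1. Keep one definition of follow-up time, first dose to last contact or death, with one stated unit.
2. Rename the 5.4 quantity *time to last disease assessment*, or delete it.
3. Label the plain summary in 8.2 as observed time on study, and keep its minimum and maximum.
4. For each expansion cohort, and for the escalation part pooled but not for single dose-level cohorts, add median follow-up by reverse Kaplan-Meier with a 95% CI. Deaths are censored; subjects alive at last contact or cut-off count as events.
5. State that if this median cannot be estimated, the observed range is reported instead.

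The cost is a few lines of SAP text and one further Kaplan-Meier call per cohort with the censoring flag reversed; SAP 10.2.1 already specifies the procedure. No new data are needed. The drawback is that the reverse Kaplan-Meier median may be imprecise or not estimable when most of a 20-subject cohort has died.

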8.3 Trial-Related Procedures, Brain Scans, and Lumbar Punctures

Trial-related procedures, brain scans, scans of other organs, and lumbar punctures will be listed chronologically by subject.

9 Medications and Therapies

9.1 Prior and Concomitant Medications

Medications are coded according to WHODRUG and stored with Anatomical Therapeutic Class (ATC) codes and generic names.

Medications will be classified as prior if the stop date and/or time was before the first dose of trial medication, and concomitant if begun after the first dose of trial medication or continuing to be used after the first dose of trial medication. Missing or partly missing stop dates will be imputed using the rules defined in Section 5.7, where applicable.

The number and frequency of concomitant medications will be summarized using therapeutic subgroup (ATC Level 2). If a subject has received more than 1 medication within an ATC level, he/she will be counted only once for that ATC level.

All prior and concomitant medications will be listed. Medications recorded as “pre-medications” on the CRFs will also be listed separately.

9.2 Subsequent Anti-Cancer Therapies

Subsequent anti-lymphoma therapies (initiated after first dose administration of GEN3009) will be categorized using WHODRUG, and summarized by ATC Level 2 and preferred term.

The time to next anti-lymphoma therapy will be summarized as per Section 10.2.5. Missing or partly missing stop dates will be imputed using the rules defined in Section 5.7, where applicable.

9.3 Diagnostic/Medical Treatment Procedures

Non-protocol specified procedures will be listed by subject.

9.4 New Tumor-Directed Surgery

All new tumor directed surgery related to the disease will be coded using MedDRA, and will be listed by subject.

10 Efficacy

The primary endpoint is the Overall Response Rate (ORR) using the Lugano criteria (for lymphoma) or iwCLL criteria (for CLL/SLL).

Response assessment will be conducted locally by investigators during the Dose Escalation part.

During the Dose Expansion part, assessments will be performed both by the investigators and IRC, where the primary endpoint will be based on investigator assessment.

The secondary efficacy endpoints include: Duration of Response (DOR), Complete Response Rate (CRR), Progression-free Survival (PFS), Overall Survival (OS), Time to Response (TTR), Time to Next anti-lymphoma Therapy (TTNT), and Minimal Residual Disease (MRD) rate.

Individual subject status over time will be presented via a swim lane plot. This figure may be split into separate plots based on cohort, stage, or subject characteristics as appropriate. Separate figures will be presented for assessments, by diagnosis cohort.

No statistical testing will be performed to evaluate the difference between diagnosis cohorts. Each cohort will be analysed independently of the other.

10.1 Primary efficacy analysis

The primary efficacy endpoint for the Dose Expansion part of this trial is the objective response rate (ORR), using the Lugano criteria for lymphoma and iwCLL for CLL. The ORR is considered a secondary efficacy endpoint for the Dose Escalation part. The main analysis of ORR will utilize the FAS.

10.1.1 Calculation of the Objective Response Rate

The ORR and its 95% confidence interval, based on Clopper-Pearson methodology, will be presented for each cohort.

The ORR and confidence interval will be calculated as per the following pseudocode:

```
PROC FREQ data=xxx;
  TABLE response / BINOMIAL (EXACT P=p0) ALPHA = 0.05 ;
  ODS output BINOMIALPROP=xxx
        BINOMIALCLS=xxx;
run;
```

The interim analysis for the Dose Expansion part shall be conducted as described in Section 14, to evaluate safety data. No analysis of efficacy data is planned at that time. Therefore, no adjustment to alpha spending for the final analysis will be performed.

Handling of missing data

No imputation of overall response will be performed. subject

Sensitivity and Robustness Analyses

In order to assess the treatment effect using different assumptions from those in the FAS analysis, the following analyses may also be performed at the final analysis for the Dose Expansion part:

- Evaluation of ORR as assessed by IRC
- Evaluation of ORR as assessed by the Investigator, using EFF set
- Evaluation of ORR as assessed by the IRC, using EFF set

10.2 Secondary efficacy analyses

The secondary analyses, including analysis of DOR, CR, PFS and TTR, are described below. As with the primary endpoint, response assessments are conducted by investigators in the Dose Escalation and Dose Expansion parts, and may also be conducted by the IRC in the Dose Expansion part. Endpoints based on response per IRC may be used for sensitivity analyses.

10.2.1 Duration of response

DOR will be derived for all subjects achieving treatment response. The number of subjects achieving treatment response, as well as the numbers subsequently achieving progressive disease or death, and the number censored, will be presented by cohort. Subjects without a documented progression or death will be censored following the rule laid out in Section 5.3.1.

The median DOR and its 95% confidence interval based on Kaplan-Meier estimates will be presented, as well as the first and third quartiles and their confidence intervals. DOR will also be presented graphically, using Kaplan-Meier curves.

The proportion of subjects with ongoing response, together with their 95% confidence intervals, will be calculated at monthly intervals starting at 1 month, based on Kaplan-Meier methodology.

The following pseudocode will be used to analyze duration of response and other similar times to event:

```
PROC LIFETEST data=xxx OUTSURV=s1 TIMELIST=xx CONFTYPE=loglog;
  WHERE COHORT=xxx;
  TIME survtime*censor (xxx) ;
  ODS OUTPUT QUARTILES=q1;
  run;
```

10.2.2 Complete response/complete remission rate

CR rate is defined as the proportion of subjects with CR as best overall response. The CR will be reported jointly with the ORR, and using the same methodology as for the ORR.

10.2.3 Progression-free survival

PFS will be summarized, analysed, and presented graphically as described for DOR. Subjects without a documented progression or death will be censored following the rule laid out in Section 5.3.1.

If feasible, PFS analysis may be also stratified by overall MRD status (negative or positive as per definition in Section 10.2.7)

